Grade 3 toxicity (recurrence of same AE)	Interrupt study treatment, initiate optimal supportive care and causality investigation. Maximum treatment interruption is 28 days. When toxicity has resolved or is resolving (Grade ≤ 2 or returns to baseline), consider re- starting AZD7648 with 1 dose reduction and prophylactic treatment (if appropriate). After 2 dose reductions, consider permanent discontinuations of AZD7648 for Grade 3 events.
Grade 4 toxicity (recurrence of same AE)	Patients should permanently discontinue AZD7648.

Table 6 Management of AZD7648 treatment related toxicity

Table 7Dose modification of study treatment AZD7648

First dose reduction	Previously determined "acceptable safety" dose level.
Second dose reduction	Previously determined "acceptable safety" dose level.
Third dose reduction	Consider permanent discontinuation of AZD7648 unless the patient is deriving clinical benefit.

Patients enrolled into the first 3 dose cohorts are permitted to dose reduce to the previous dose cohort, but must discontinue if a dose reduction is required in the first dose level.

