8.3.2 Time period and frequency for collecting AE and SAE information

AEs will be collected from time of signature of ICF throughout the treatment period and including the 28-day follow-up visit after treatment discontinuation.

All SAEs will be recorded from the time of signing of ICF until the 28-day follow-up visit after treatment discontinuation. Only SAEs related to the study treatment and/or procedure will be recorded thereafter (during the progression follow-up).

All SAEs will be recorded and reported to the Sponsor or designee within 24 hours, as indicated in Appendix B. The Investigator will submit any updated SAE data to the Sponsor within 24 hours of it being available.

Investigators are not obligated to actively seek AE or SAE in former study patients. However, if the Investigator learns of any SAE, including a death, at any time after a patient's last visit and he/she considers the event to be reasonably related to the study treatment or study participation, the Investigator may notify the Sponsor.

The method of recording, evaluating, and assessing causality of AE and SAE and the procedures for completing and transmitting SAE reports are provided in Appendix B.

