3.2.1.4 Adverse Events

Adverse events (AEs) and serious adverse events (SAEs) will be collected throughout the study, from date of informed consent until 28 days after the last dose of study treatment. Events will be defined as treatment emergent if they onset, or worsen (by investigator report of a change in intensity), during the

treatment period starting from the first dose on cycle 0, day 1 or during the 28-day safety follow-up period. Any events in this period that occur after a patient has received further therapy for cancer (following discontinuation of study treatment) will be flagged in the data listings. The latest version of MedDRA will be used to code the AEs. AEs will be graded according to the National Cancer Institute of Common Terminology Criteria for AEs (CTCAE version 5.0 or higher).

In general, all AE summary tables include only treatment emergent AEs. AEs occurring prior to dosing or starting more than 28 days after discontinuation of study drug will be flagged in listings and will not be included in any summaries.

All reported AEs will be listed along with the actual treatment received at the time of onset, date of onset, date of resolution (if AE is resolved), investigator's assessment of CTCAE grade, relationship to study treatment, action taken and outcome. Frequencies and percentages of patients reporting each preferred term will be presented (i.e., multiple events per patient will not be accounted for, except for event level summaries).

Summaries of adverse events (the number and percentage of patients by treatment) by MedDRA System Organ Class (SOC) and Preferred Term (PT) will include but are not limited to:

- All AEs.
- All AEs possibly related to study treatment.
- AEs of CTCAE grade 3 or higher.
- AEs of CTCAE grade 3 or higher, possibly related to treatment.
- AEs with outcome of death.
- All SAEs.
- All SAEs possibly related to study treatment.
- AEs leading to discontinuation of treatment.
- AEs leading to discontinuation of treatment, possibly related to treatment.
- SAEs leading to discontinuation of treatment.
- SAEs leading to discontinuation of treatment, possibly related to treatment.

Other significant adverse events (OAE)

No OAEs are planned to be defined for this study.

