Any AE occurring within the defined 28 days follow-up period after discontinuation of investigational product will be included in the AE summaries. Any adverse events in this period that occur after a patient has received further therapy for cancer (following discontinuation of investigational product) will be flagged in the data listings. TEAEs occurring prior to first dose of investigational product (ie, before study Day 1) which subsequently worsen in severity following dosing will be presented in the summary tables. All other AEs occurring prior to first dose of investigational product (ie, before study Day 1), or after the 28 days follow-up period after discontinuation of investigational product will be listed separately, but not included in the summaries.

Fluctuations observed in CTCAE grades during study will be listed (where collected). When assigning a maximum CTCAE grade to a TEAE, only grade changes occurring after the date of first dose of study treatment and up to 28 days after the last dose of study treatment will be considered.

Details of any deaths will be listed for all patients.

Haematology and clinical chemistry results will be summarised using descriptive statistics (mean, median, standard deviation, minimum, maximum and number of observations). For all laboratory variables included in the current version of CTCAE, the CTCAE grade will be summarised. The post-baseline results and its change from baseline for laboratory, ECG, vital signs data at each timepoint will be summarised. For all haematology and clinical chemistry results, change from baseline will be plotted using a spaghetti plot. Creatinine clearance and echocardiogram (LVEF) results at different timepoints and their change from baseline will be summarised using descriptive statistics. Creatinine clearance and echocardiogram (LVEF) results will be listed as well by visit. LVEF will also be summarised by categories listed in section 3.2.1.12. All abnormal findings from the physical exam will be listed. The number of patients for each ECOG-PS grade will be presented.

For the core module, individual 4 β -hydroxy cholesterol concentration data will be listed only.

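### SAP 4.2.1 summarises adverse events to 28 days after discontinuation but caps their maximum CTCAE grade at 28 days after the last dose, so a late rise in grade can be tabulated too low

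*SAP*

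**What the plan says.** **Inclusion in summaries.** SAP 4.2.1: "Any AE occurring within the defined 28 days follow-up period after discontinuation of investigational product will be included in the AE summaries". Later events are set aside by the matching rule: "or after the 28 days follow-up period after discontinuation of investigational product will be listed separately, but not included in the summaries". Both count from discontinuation, as does protocol 9.4.2.

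**Maximum grade.** The next paragraph of SAP 4.2.1 counts from the other date. Only grade changes after first dose and "up to 28 days after the last dose of study treatment will be considered".

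**SAP 3.2.1.4** uses both dates:
- Collection runs "from date of informed consent until 28 days after the last dose of study treatment".
- The exclusion rule covers AEs "starting more than 28 days after discontinuation of study drug will be flagged in listings".
- The treatment-emergent definition covers the treatment period "or during the 28-day safety follow-up period" and does not say which date starts those 28 days.

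**Protocol 8.3.2** collects AEs through the treatment period, "including the 28-day follow-up visit after treatment discontinuation". SAP Table 4 also places the safety follow-up visit 28 days (±7) after investigational product discontinuation.

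**Dose interruption.** Protocol 6.6, Table 6, for Grade 3 to 4 toxicity: "Maximum treatment interruption is 28 days". Section 6.6 also requires AZD7648 to be discontinued if the toxicity has not recovered to the stated level within 28 days of onset.

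**The concern.** The rule that selects an AE for a table and the rule that grades it should close on the same day. Here they close on different days whenever treatment is formally discontinued some time after the last tablet or infusion. The protocol expects that situation: a patient is held for toxicity, does not recover in the permitted time and is then taken off treatment. On an intermittent schedule it can happen without any unplanned hold.

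Safety is the primary objective, and the current SAP has been cut back to concentrate on it. AEs by CTCAE grade, and AEs of Grade 3 or higher, are core outputs by cohort. Removing late values from a maximum can lower it or leave it unchanged, but never raise it, so any error makes the drug look milder. Core Module cohorts hold 1 to 6 patients and combination cohorts 3 to 6. One re-graded event therefore moves a cohort's proportion by 1/6 (17%) with six patients or 1/3 (33%) with three. Two programmers could also build different tables from the same text.

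**Working it through.** The plan gives no figure to reproduce. The check is a comparison of the rules and date arithmetic.

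**Inputs**
- Grading window ends 28 days after the last dose (SAP 4.2.1).
- Inclusion window ends 28 days after discontinuation (SAP 4.2.1, SAP 3.2.1.4, protocol 9.4.2).
- Longest permitted interruption: 28 days (protocol 6.6).
- Planned undosed days on the 7-days-on schedule: 21 (SAP 3.2.1.1, Z=21).

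**Formula.** Let the last dose be Day 0 and discontinuation Day L.
- Grading window ends on Day 28.
- Inclusion window ends on Day L + 28.
- Gap = (L + 28) − 28 = L days.
- Share of the post-discontinuation follow-up in which a grade change does not count = L/28.

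| L (days) | Inclusion ends | Grading ends | Gap (days) | L/28 |
|---|---|---|---|---|
| 0 | Day 28 | Day 28 | 0 | 0% |
| 7 | Day 35 | Day 28 | 7 | 25% |
| 14 | Day 42 | Day 28 | 14 | 50% |
| 21 | Day 49 | Day 28 | 21 | 75% |
| 28 | Day 56 | Day 28 | 28 | 100% |

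L = 21 is a patient on the 7-days-on schedule who takes the Day 7 dose and is discontinued at the end of the 28-day cycle (28 − 7 = 21). L = 28 is a patient discontinued at the end of the longest interruption; the grading window then closes on the day of discontinuation. I treat the two situations separately and do not add them together.

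**What each rule does, with L = 28**
1. *Grade 3 at Day 0, unresolved at Day 28, Grade 4 on Day 35.* The event is included. The change on Day 35 falls after Day 28 and is ignored, so the table shows Grade 3 instead of Grade 4. The Grade 3 or higher count does not change.
2. *A Grade 2 event in the same patient that first reaches Grade 3 on Day 35.* The event is included but tabulated as Grade 2. Here the Grade 3 or higher count is one event short.
3. *Grade 3 at Day 0, still Grade 3 on Day 50.* The maximum is Grade 3 under both rules. Slow resolution without worsening causes no error.
4. *New event on Day 35, Grade 3 at onset.* The event is included. The sentence restricts grade changes, and an onset grade is not naturally read as one, so Grade 3 stands. A later rise within follow-up would still be missed.

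With one anchor for both rules the gap is 0 days for every L.

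**The case against.** **The two dates may be meant as one.** For a patient who stops during an interruption, SAP 3.2.1.1 uses the last recorded administration date, and SAP 3.2.1.2 does the same for relative dose intensity. Protocol 7.1.3 has the last intake date recorded. Protocol 8.3.11, on reporting deaths, describes the follow-up period as running from the last dose, so the protocol is not uniform either. If discontinuation meant last administration everywhere, the gap would vanish. This does not cure the conflict. The SAP rules belong to exposure and dose intensity, and nothing extends them to AEs. Extending them would shorten the window that protocol 8.3.2 and 9.4.2 set from discontinuation, and SAP section 6 declares no such change.

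**Stronger readings that do not hold.** A reader might infer that AEs are dropped from the tables. Every explicit inclusion or exclusion rule counts from discontinuation, so omission would need the last-dose wording to be programmed into the unanchored treatment-emergent definition. A reader might also infer that late-onset events have no usable grade, or that slow-resolving toxicities as a class are under-graded. Cases 3 and 4 above show that neither follows.

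**The impact is limited.** This stands in part. Safety is descriptive. Dose-limiting toxicities are those agreed by the Safety Review Committee over Cycles 0 and 1, so dose decisions are untouched. Serious AEs, fatal AEs and AEs leading to discontinuation have their own tables. Grade fluctuations are listed where collected, so a late rise can still be seen there. Development has been halted and the report is abbreviated. None of this makes the maximum-grade table right.

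**Conclusion.** The conflict is in the text, and the maximum-grade rule is wrong as written. An AE that the SAP includes, and whose grade rises more than 28 days after the last dose but within 28 days after discontinuation, is tabulated below its true maximum. The gap is L days: up to 28 after an interruption, about 21 on the 7-days-on schedule, and nil when discontinuation coincides with the last dose. Any error is downward. The Grade 3 or higher count is affected only when the event first reaches Grade 3 in the gap.

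This rests on two assumptions: that discontinuation is dated when treatment is formally stopped, as the distinction from last dose in SAP 3.2.1.1 implies, and that the grading sentence is programmed literally. The documents give no basis for estimating how many patients are affected; it may be few or none. The change is worth making because the endpoint is primary and the correction is small.

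**What to change.** - **SAP 4.2.1:** end the maximum-grade window at the end of the protocol's 28-day follow-up after discontinuation of study treatment, in place of the last-dose cut-off.
- **SAP 3.2.1.4:** use the same anchor in the collection sentence, to agree with protocol 8.3.2, and name it in the treatment-emergent definition.

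**Cost.** A wording edit and one derivation. No new data are needed, because protocol 8.3.4 already collects grade changes with their dates. The downside is that a few later grade changes, some possibly unrelated to treatment, enter the tables. Those more than 28 days after the last dose can be flagged in the listings.

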3 OBJECTIVES AND ENDPOINTS

Primary objective:	Endpoint/Variable:							
To investigate the safety and tolerability of AZD7648	Adverse events (AEs)/serious adverse events (SAEs)							
when given orally to patients with advanced	DLTs							
malignancies, as monotherapy and in combination	Physical examination							
with anti-cancer agents, and define the doses and schedules for further clinical evaluation	Eastern Cooperative Oncology Group performance status (ECOG PS)							
	Vital signs							
	Electrocardiogram (ECG) and Echocardiogram							
	(ECHO; Combination Module 1 only)							
	Laboratory data							
Secondary objectives:	Endpoint/Variable:							
To characterise the PK of AZD7648, following a single dose and at steady state after multiple dosing, when given orally as monotherapy and in combination with anti-cancer agents. To characterise the effect of food on AZD7648 exposure (if conducted)	Area under the curve (AUC) and/or AUC_{0-t} after a single dose and AUC_{tau} after multiple doses. Maximum plasma concentration (C_{max}) after a single dose and $C_{max,ss}$ after multiple doses Time to reach maximum plasma concentration (t_{max}) Minimum plasma concentration at steady state ($C_{min,ss}$) Half-life ($t_{1/2}$)							
	Dose proportionality							
	AUC _{0-t} and C _{max} ratio for food effect							
To understand the cytochrome P450 3A4 (CYP3A4) induction potential of AZD7648	Post-dose to pre-dose 4-β-hydroxy cholesterol ratio							
To obtain a preliminary assessment of anti-tumour	Radiological response evaluated using response							
activity of AZD7648 as monotherapy and in	evaluation criteria in solid tumours (RECIST) 1.1							
combination with anti-cancer agents	• Percentage best change in target lesion (TL)							
	Duration of response							
	• Objective response rate (ORR)							
	• Progression-free survival (PFS)							
	• Overall Survival (OS) (Part B only)							

Table 2Study objectives

Tertiary/Exploratory objectives:	Endpoint/Variable:
	CCI
CCI	CCI CCI CCI
CCI	CCI

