8.5.1 Determination of drug concentration

Samples for determination of AZD7648 and PLD (as total doxorubicin) concentrations in plasma, and AZD7648 concentrations in urine will be analysed by Covance on behalf of AstraZeneca, using appropriate bioanalytical methods. Full details of the analytical methods used will be described in a separate Bioanalytical Report.

All samples still within the known stability of the analytes of interest (ie, AZD7648 and PLD,) at the time of receipt by the bioanalytical laboratory will be analysed.

In addition, the PK samples may be subjected to further analyses in order to further investigate the presence and/or identity of drug metabolites. Any results from such analyses will be reported separately from the CSR.

8.5.2 Determination of 4β-hydroxy cholesterol concentrations for assessment of CYP3A4 induction potential

Blood samples will be collected from all patients at pre-dose of Cycle 0, Day 1; Cycle 1, Day 8, and Cycle 2, Day 1 in the AZD7648 monotherapy for the determination of 4β -hydroxy cholesterol concentrations in plasma. Analysis of 4β -hydroxy cholesterol will be performed by Covance on behalf of AstraZeneca, using an appropriate bioanalytical method. Full details of the analytical methods used will be described in a separate Bioanalytical Report.

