1.2 List of modules

The following modules for the study are included within this SAP.

Core Module: AZD7648 Monotherapy. Part A, dose escalation

Combination Module 1: AZD7648 + PLD. Part A, dose escalation.

For the endpoints included in the safety, efficacy and exploratory objectives, see [Table 1](#).

Table 1 : Study objectives and endpoints

Primary objective (Safety):	Endpoint/Variable:
To investigate the safety and tolerability of AZD7648 when given orally to patients with advanced malignancies, as monotherapy and in combination with anti-cancer agents, and define	
 • Adverse events (AEs)/serious adverse events (SAEs) • Dose limiting toxicities (DLTs) • Physical examination

the doses and schedules for further clinical evaluation.
	
 • Eastern Cooperative Oncology Group performance status (ECOG PS) • Vital signs • Electrocardiogram (ECG) and Echocardiogram (ECHO; applicable for Combination Module 1 only) • Laboratory data

Secondary objectives:
	
Endpoint/Variable:

To characterise the PK of AZD7648, following a single dose and at steady state after multiple dosing, when given orally as monotherapy and in combination with anti-cancer agents.
	
 • Area under the curve to infinity (AUC_{inf}) and/or AUC_{last} after a single dose and AUC_∞ after multiple doses. • Maximum plasma concentration (C_{max}) after single and multiple doses. • Time to reach maximum plasma concentration (t_{max}) • Minimum plasma concentration at steady state (C_{min}) • Half-life (t_{1/2λz}) • Accumulation ratio (R_{ac}) • Dose proportionality (TCP) • AUC_{last} and C_{max} ratio for food effect (applicable for food effect cohort only in the Core module expansion phase) • Other PK parameters may also be estimated

^[a]To understand the cytochrome P450 3A4 (CYP3A4) induction potential of AZD7648
	
Post-dose to pre-dose 4β-hydroxy cholesterol ratio (only for AZD7648 Core Module)

To obtain a preliminary assessment of anti-tumour activity of AZD7648 as monotherapy and in combination with anti-cancer agents
	
Radiological response evaluated using response evaluation criteria in solid tumours (RECIST 1.1)
 
 • Percentage best change in target lesion (TL)

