Pharmacodynamics set	All patients who received at least 1 dose of of any study treatment with at least one reportable pharmacodynamic measurement

^[a] Measurable disease is defined as having at least one measurable target lesion, not previously irradiated, which is ≥ 10 mm in the longest diameter (LD) (except lymph nodes which must have short axis ≥ 15 mm).

^[b] This will be derived directly from the most recent safety review committee meeting minutes prior to data cut off.

Upon database release for each module, protocol deviations and analysis set outputs will be produced and will be sent to AZ for review. Prior to database lock, an analysis set classification meeting will be arranged to discuss the outputs and decide which patients and/or patient data will be excluded from certain analyses. Decisions made regarding the exclusion of patients and/or patient data from analyses will be made prior to database hard lock and will be documented and approved by AZ.

A summary on which analysis set will be used for each outcome variable is provided in [Table 3](#).

Table 3: Summary of outcome variables and analysis sets

Outcome variable	Analysis Sets
Disposition	Enrolled
Demography and baseline characteristics	Safety
Safety data	
Exposure	Safety
Adverse Events	Safety
Prior/Concomitant Medication	Safety
Laboratory measurements	Safety
Vital Signs/ECG/Physical examination	Safety
Echocardiogram	Safety
ECOG PS	Safety
DLTs	DLT evaluable set
4 β -hydroxy cholesterol ratio in plasma	Pharmacokinetics set
Efficacy Data	
Best Objective Response	Evaluable for objective response set Evaluable for efficacy set
Objective Response Rate	Evaluable for objective response Evaluable for efficacy set
Change in tumour size	Evaluable for objective response
Duration of Response	Evaluable for objective response Evaluable for efficacy
PFS	Safety /Evaluable for efficacy
Overall survival	Safety
Pharmacokinetics	
Pharmacokinetic concentrations and parameters	Pharmacokinetics set
Pharmacodynamics	
PDc analysis will be presented in a separate document.	PDc related population will be defined in a separate document dedicated to PDc.
Exploratory biomarkers	

Outcome variable	Analysis Sets
CCI [REDACTED]	CCI [REDACTED]
CCI [REDACTED]	

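### The SAP keeps the 4β-hydroxycholesterol ratio as its CYP3A4-induction endpoint but plans only a concentration listing, and does not declare the ratio dropped

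*SAP*

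**What the plan says.** Protocol Section 3 (Table 2) sets a secondary objective on the CYP3A4 induction potential of AZD7648, with a single endpoint: "Post-dose to pre-dose 4-β-hydroxy cholesterol ratio". For the monotherapy module, Protocol 8.5.2 plans blood samples "collected from all patients at pre-dose of Cycle 0, Day 1; Cycle 1, Day 8, and Cycle 2, Day 1". This gives one drug-free baseline and two on-treatment values per patient.

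The current SAP repeats the endpoint in Table 1 (Section 1.2): "Post-dose to pre-dose 4β-hydroxy cholesterol ratio (only for AZD7648 Core Module". Table 3 (Section 2.2) lists "4 β -hydroxy cholesterol ratio in plasma" as an outcome variable and assigns it to the pharmacokinetics set.

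The sections that should deliver it do not. SAP 3.2.1.9 provides individual concentrations by cohort and visit, in a listing. SAP 4.2.1 closes with the statement that, for the core module, the "cholesterol concentration data will be listed only". The ratio is not among the derived parameters in 3.2.2.2 and has no summary in 4.2.3. Section 6, on changes from the protocol, covers only renamed PK symbols and a pointer to additional PK parameters.

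**The concern.** A named secondary endpoint has an analysis set but no definition, no summary and no declared removal. Someone programming from Tables 1 and 3 would expect a ratio; someone programming from 3.2.1.9 and 4.2.1 would produce a listing. Following the methods sections, the study report would contain no estimate for an objective it still states.

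If a ratio were later computed from the listing, the visit, the treatment of incomplete pairs, the scale and any exclusions would all be chosen after seeing the data. The subject is not idle: Protocol 5.3.3 limits contraceptive choice because of a potential CYP3A4 interaction, and the 4β-hydroxycholesterol ratio is the only endpoint the study designates for induction.

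**Working it through.** **Step 1: compare the places that mention the marker.**

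- Protocol Table 2: endpoint is the ratio.
- SAP Table 1: endpoint is the ratio, core module only.
- SAP Table 3: outcome variable is the ratio, pharmacokinetics set.
- SAP 3.2.1.9: concentrations, listed.
- SAP 4.2.1: concentrations, listed only.
- SAP 3.2.2.2 and 4.2.3: ratio absent.
- SAP Section 6: no entry.

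Three planned samples give two possible ratios per patient, Cycle 1 Day 8 over Cycle 0 Day 1 and Cycle 2 Day 1 over Cycle 0 Day 1. The SAP derives neither.

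**Step 2: check whether the scope cut explains it.** SAP 1.1 says outputs were reduced after development was halted. The edition 4.0 entry in the version history records removal of the summary of 4β-hydroxycholesterol concentrations. It says nothing about removing the ratio endpoint.

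**Step 3: what a summary could show.** The plan has no precision figure for this endpoint to reproduce. The documents give neither a variance nor the number of patients with paired samples; Protocol 9.2 plans about 46 evaluable patients in core escalation, in cohorts of 1 to 6. The inputs below are therefore assumptions: a within-patient CV of 15% to 35%, and 20 to 40 pairs for a pooled estimate.

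With independent errors on the two occasions, the SD of a log ratio is √(2·ln(1+CV²)):

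- CV 15%: √(2·ln 1.0225) = 0.211
- CV 35%: √(2·ln 1.1225) = 0.481

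The 90% half-width on the log scale is t(0.95, n−1)·SD/√n. Exponentiating gives the limits relative to the estimated geometric mean ratio.

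| Pairs | t | CV | Log half-width | Upper limit | Lower limit |
|---|---|---|---|---|---|
| 40 | 1.685 | 15% | 0.056 | +6% | −5% |
| 40 | 1.685 | 35% | 0.128 | +14% | −12% |
| 20 | 1.729 | 15% | 0.082 | +9% | −8% |
| 20 | 1.729 | 35% | 0.186 | +20% | −17% |
| 6 | 2.015 | 15% | 0.174 | +19% | −16% |
| 6 | 2.015 | 35% | 0.395 | +49% | −33% |
| 3 | 2.920 | 15% | 0.356 | +43% | −30% |
| 3 | 2.920 | 35% | 0.810 | +125% | −56% |

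The first four rows describe a ratio pooled over all doses and over any intermittent schedules used (Protocol 6.1.2 allows these from Cohort 2). The last four describe single regimens. Under SAP 4.1, a regimen with fewer than three patients shows only the count, minimum and maximum.

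**The case against.** The strongest reply is that this is a deliberate scope cut. Development was halted, SAP 2.1 plans an abbreviated report, and the version history names the 4β-hydroxycholesterol summary as removed. Tables 1 and 3 also still carry other discontinued items (the food-effect ratio and overall survival), so the ratio may simply not have been pruned. That may well be so, but what was declared removed is a summary of concentrations. If the ratio was meant to go too, Tables 1 and 3 need correcting and Section 6 needs a line. PK outputs were reduced rather than abandoned: accumulation ratios, the temporal change parameter and renal clearance are still derived.

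Several stronger readings are tempting, and the documents do not support them.

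- *That the trial has no other clinical evidence on induction.* Protocol Table 5 names CYP3A4 as the principal enzyme metabolising AZD7648, and SAP 3.2.2.2 derives within-patient accumulation ratios and the temporal change parameter. These could show auto-induction indirectly, although they are not the endpoint for this objective.
- *That between-patient variation hides the change in a listing.* The listing is individual and by visit, so a reader can work out each patient's ratio. What is missing is a planned derivation and summary.
- *That the samples have already been assayed.* Protocol 8.5.2 is prospective, and no count of samples or assays is given.
- *That a table would settle dose dependence.* The pooled ratio mixes doses and schedules, and regimen estimates from a handful of patients are too imprecise.

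It is also fair to say that neither document prescribes an interval for this endpoint, that the study plans no hypothesis tests, and that no documented decision, including the contraception rule, depends on the result. Finally, the text of the footnote attached to this objective in SAP Table 1 is not in the available copy, and output specifications sit in a separate document. Neither could be checked, but the wording of 4.2.1 is explicit.

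**Conclusion.** The point holds as an internal contradiction with a practical result: the SAP retains a secondary endpoint and its analysis set, plans no derivation or summary of it, and does not declare it dropped. As written, the plan gives no estimate for the CYP3A4-induction objective. It does not follow that the question cannot be answered, since the listed values would allow it.

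The size of what is lost rests on assumed inputs. With 20 to 40 pairs and a within-patient CV of 15% to 35%, the pooled 90% CI would be about ±6% to ±20%, which is a useful estimate provided readers know that it averages over doses and schedules. At 3 to 6 patients per regimen the upper limit lies about 19% to 125% above the estimate, so those results are descriptive. The primary safety analysis is unaffected.

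**What to change.** Either of two changes resolves the contradiction.

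1. **Analyse the ratio.** In SAP 3.2.1.9 and 4.2.1, define for each core-module patient in the pharmacokinetics set the ratios Cycle 1 Day 8 / Cycle 0 Day 1 and Cycle 2 Day 1 / Cycle 0 Day 1, from the pre-dose samples. State that a ratio is missing if either value is missing. Add both ratios to the planned listing. Summarise the geometric mean ratio on the log scale with a confidence interval (90% was used above; the level is a choice) over all patients, noting that it pools doses and schedules. Summarise by dose regimen descriptively, under the n ≥ 3 rule in SAP 4.1.
2. **Drop it openly.** Remove the ratio from SAP Tables 1 and 3 and state in Section 6 that this protocol endpoint will not be analysed, with the reason.

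The first option costs one paired derivation at two visits and one small table, from values the SAP already plans to list. The second costs a few lines of text. The first is preferable because it answers a stated objective for very little work.
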